HMC RESEARCH PROTOCOL

Nurse-led medication self-management intervention in the improvement of medication adherence in adult patients with multi-morbidity: A Feasibility Randomized controlled trial

[name]

[name]

Date-2 Nov 2022

NCT- Not available

1. Summary

Back ground & Aims

Adult patients suffering from multimorbidity are at high risk of medication non-adherence. It has been well established that self-management support is an effective strategy to enhance medication adherence for patients with chronic conditions. However, little is known about the effect of the medication self-management intervention in Adult patients with multimorbidity. The aim of this study to evaluate the effectiveness of a nurse-led medication self-management intervention in improving medication adherence and health outcomes in adult patients with multimorbidity.

Methods

This study is a single centre, single-blind, two-arm randomised controlled trial. Adult patients with multi-morbidity will be recruited from NCCCR Qatar. A total of 100 participants will be randomly allocated to receive standard care or standard care plus the medication self-management intervention. The intervention will be delivered by clinical nurse specialists. The 6-week intervention includes three face-to-face education sessions (2st week, 4rd week and 6th week) and two weekly (8th week and 10 week) follow-up phone calls. Participants in the control group continue to receive all respects of standard care offered by healthcare providers, including chronic disease management, drug prescription, referral to hospital specialists, health education and consultations regarding patients' diseases and treatments during centre visits.

Outcome

The primary outcome is medication adherence as measured by the 5-item Medication Adherence Report Scale. Secondary outcomes include medication self-management capacity (medication knowledge, medication beliefs, and medication self-efficacy), treatment experiences (medication treatment satisfaction and treatment burden). All outcomes will be measured at baseline, immediately post-intervention (7th week), and at 3-month post-intervention.

2. Abbreviations and Acronyms

NCCCR- National Cancer Care Center and Research

CNS- Clinical Nurse Specialist

IMB- Information-Motivation-Behavioral Skills

3. Introduction / Background

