
evoking, focusing, planning and motivational interview process. The current study aims to implement evidence-based, theoretical and nurse-led drug self-management interventions in adult patients with multi-morbidity.

4. Objectives

The primary objective

To evaluate the effectiveness of a six-week intervention led by a nurse in medication self-management to improve medication compliance in adult patients with multimorbidity and going to discharge, as compared with standard care.

[figure not shown]
Secondary objectives

To evaluate the effectiveness of the intervention on the improvement of patients' medication self-management capacity (medication knowledge, medication beliefs, and medication self-efficacy), treatment experiences (medication treatment satisfaction and treatment burden), as compared with standard care. *(Retrospective means the data is already in existence when the project is submitted to the IRB for initial (if this is a retrospective chart review, the end date must come before the submission date): mm/dd/yyyy to mm/dd/yyyy)*

5. Study Methodology

This is a single Centre open label, two-arm randomized controlled trial with 1:1 randomization at the participant level. The patient population will be patients with at least two comorbidities. The patient recruitment will be done in the National Centre for Cancer Care and Research (NCCCR) in the outpatient department in the clinical nurse specialist counselling room. Participants will randomly be allocated to receive standard care(control) and standard care plus the medication self-management intervention (Motivational Interview). Primary and secondary outcomes of study will measure better medication adherence, medication self-management capacity and treatment experiences, which will be collected from both group including the intervention group and control group (Participants in the control group will continue to receive all respects of standard care offered by healthcare providers) at baseline (T0), in the 7th week immediately post-intervention (T1), and at 3-month post-intervention (T2). This protocol is presented based on the recommendations of the Standard Protocol Items: Recommendations for Interventional Trials (SPIRIT) 2013 statement(24). The results of this trial will be reported as per the Consolidated Standards of Reporting Trials (CONSORT) 2010 statement(25).

An overview of the study design is shown in Fig. 1.

[figure not shown]

Fig. 1 CONSORT flow diagram of the study protocol

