Following recruitment, patients will be randomized to either the intervention or the control arm in a near 1:1 ratio, using a computer-generated randomized permuted block design. The design will use random block lengths of 2, 4 or 6, and include an initial unbalanced block, with a maximum of one additional patient in either arm, to further hide allocation sequences, which means that the ultimate sample size and allocation ratio will vary very slightly from what is planned depend on the unbalanced block.

Each participant will be assigned a special code generated by the computer. The randomization will be kept by the PI and CNS. After the eligibility assessment by CNS, data will be obtaining at the baseline (after completion of informed consent), 7th week and 12th week.

Intervention group

The medication self-management intervention consists of three face-to-face education sessions and two weekly telephone follow-up over 6 weeks. Intervention components are derived from an extensive review of the literature, including the related theoretical framework and current practice. Based on the extended IMB model of medication adherence, this intervention is designed to offer information related to medication treatment, motivate patients to adhere, help build medication self-management skills, and develop adherence improvement plans. The face-to-face meeting will take place in the clinical nurse specialist counselling room in NCCCR. The face-to-face sessions will include all of the following: exploration of medication treatment experience and expectation, medication knowledge education, motivation feedback tailored to the individual's personal and social barriers to adherence, medication self-

management skills building, and goal setting. A patient-centered approach will be adopted considering the complex needs of patients with various combinations of chronic conditions.

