A comprehensive assessment of adherence problems will be firstly conducted to identify the factors that affect adherence, including how and why these factors contribute to poor adherence. Medication-related knowledge and skills will be provided based on individual treatments and barriers to adherence. Motivational interviewing techniques will be used for a better understanding of patients' cognitive factors of adherence behavior. Nurses will discuss with patients to explore their preferences and priorities in medication treatments, setting goals that are practical and acceptable for addressing their problems in medication use, and develop individualized adherence improvement plan to reach these goals. Taking patients' complexity into account, strategies to reduce treatment burden will also be incorporated into intervention sessions, including prioritizing medication and other self-management activities using shared decision making, providing communication skills with healthcare providers and encouraging patients to discuss with the physicians about burdensome regimens, exploring patients' family and social network to support their self-care, and helping them to incorporate self-care activities into daily life. Each face-to-face session will last approximately 30–40 min and will be delivered individually in NCCCR by CNSs. The duration of each session can be adjusted by CNSs in accordance with the patients' barriers and problems to medication adherence. The three face-to-face sessions are designed to complete at 7–10-day intervals over 4 weeks. Before the first face-to-face session, nurses will review patients' clinical health records to confirm the screening criteria.

Patients will be asked to bring all medications to HMC. After the conclusion of the last face-to-face session, education materials containing instructions and information on the name, purpose, side effects, and special tips for each usual chronic medication and medication skills will be provided to participants. After the face-to-face sessions, patients are followed up by two weekly by telephone. Each telephone encounter lasted 10–20 min. The aim, content, and delivery strategy of each session are shown in Table 1.

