Based on screening & randomization tool

Risk

In this section describe the anticipated risks associated with participation in the research (i.e. illness, injury, death)

No risk is anticipated as part of study

Bio-Specimens & Sample Collection

In this section describe what specimens or samples will be collected specifically for research, if specimens will be stored long-term and/or destroyed. Consider what happens to data/specimens if subject withdraws consent

NA

Outcomes

In this section provide details on the outcome measures and the anticipated primary & secondary outcomes

Outcome assessment

The nurses masked to the participant allocation will collect follow-up data through telephone interview. Participants will be assessed at baseline (T0), in the week immediately post-intervention (7th week) (T1), and at 3-month post-intervention (T2). Table 2 provides an overview of primary and secondary outcomes as well as covariates at each time point. Permission will be obtained from the original authors to use the scales for this study.

Primary outcome

Medication Adherence

The English version of Morisky-8 will be administered to assess medication adherence of the participants(29). The Morisky-8 is a self-reporting measure of unintentional and intentional medication non-adherent behaviors with a yes and no response. The total score of the moresky-8 ranges from 0 to 8, with a higher score representing higher adherence to medication.

Table 2 Schedule of enrolment, interventions, and assessments

TIMEPOINT	STUDY PERIOD				
	Enrolment	Baseline T0	Intervention	Follow-up	
				T1	T2
ENROLMENT					
Eligibility screen	X				
Informed consent	X				
Allocation		X			
INTERVENTION					
Intervention group			X		
Control group			X		
ASSESSMENTS					
Primary outcome					
Medication adherence (Moresky-8)		X		X	X
Secondary outcomes					
Medication knowledge (PKMUQ)		X		X	X
Medication beliefs (BMQ)		X		X	X
Medication self-efficacy (SEAMS)		X		X	X
Treatment burden (TBQ)		X		X	X
Potential covariates					

Socio-demographics questionnaire)	(Patients	X
Number of prescribed medications (one-item question)		X
Depressive symptoms (PHQ-9)		X

Secondary

outcomes

Medication Knowledge

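### The protocol gives incompatible intervention schedules, so it is unsettled whether week 7 (T1) follows the intervention and when T2 falls

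*Combined protocol and SAP*

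**What the plan says.** On the schedule of contacts:

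- Section 1 (Summary, Methods) says that a 6-week intervention includes "three face-to-face education sessions (2st week, 4rd week and 6th week) and two weekly (8th week and 10 week) follow-up phone calls".
- Section 6 (Intervention group) says that the intervention "consists of three face-to-face education sessions and two weekly telephone follow-up over 6 weeks".
- The same subsection adds: "The three face-to-face sessions are designed to complete at 7–10-day intervals over 4 weeks". It puts the calls after the sessions and again describes them as *two weekly*.
- Table 1 lists the telephone follow-up among the intervention sessions, with its own aims and content: feedback on performance, difficulties in applying the skills, and more adherence education if needed. Its row label speaks of a 2-week follow-up.
- Section 4 states the primary objective for a six-week intervention.

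On the assessments:

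- Section 1 (Outcome): "All outcomes will be measured at baseline, immediately post-intervention (7th week), and at 3-month post-intervention".
- Section 5: "in the 7th week immediately post-intervention (T1), and at 3-month post-intervention (T2".
- Section 7 (Outcome assessment) places T1 "in the week immediately post-intervention (7th week) (T1", with T2 three months after the intervention.
- Section 6 (Randomization & blinding) gives baseline, week 7 and week 12, without tying either week to the end of the intervention.
- Section 6 (Sample size) bases the calculation on medication adherence at 3 months of follow-up.

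**The concern.** T1 is named by its relation to the end of the intervention, but the protocol does not give one end. If the Summary's weeks are followed, two planned contacts come after the assessment that is supposed to follow them. Those contacts are not passive follow-up. Section 6 counts them as part of what the intervention consists of, Table 1 gives them educational content, and Section 7 (Intervention fidelity and contamination) has nurses log them alongside the face-to-face sessions.

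Three things are at stake:

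- **Interpretation of T1.** The objective concerns the effect of the whole intervention. A T1 contrast taken before the calls estimates the effect of the face-to-face sessions only. Section 8 analyses the repeated measures together by generalized estimating equations and names no single primary time point, so T1 enters the analysis of the primary outcome.
- **Date of T2.** T2 is also defined from the end of the intervention, so the same ambiguity reaches the time point on which the sample size is based.
- **Fidelity.** Section 7 provides for retraining when delivery departs from the protocol. Whether contact dates depart from it cannot be judged against two different schedules.

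**Working it through.** No sample-size formula applies; the check is arithmetic on the stated weeks. It assumes that all week numbers share one origin, which the protocol does not state outright.

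**1. Can the stated 6 weeks be reproduced?** From Section 6, yes: sessions over 4 weeks plus two calls 7 days apart give 4 + 2 = 6 weeks. From the Summary, no: the contacts are in weeks 2, 4, 6, 8 and 10, so the last is in week 10.

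**2. Contacts before T1 on the Summary's weeks.** With T1 in week 7:

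- before T1: weeks 2, 4, 6 = 3 of 5 (60%)
- after T1: weeks 8, 10 = 2 of 5 (40%), by 8 − 7 = 1 week and 10 − 7 = 3 weeks

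**3. Contacts before T1 on the Section 6 schedule.** Last call (day) = s + 2i + 2c, where s is the day of the first session (assumed 0, 7 or 14), i the session interval (7 or 10 days, as stated) and c the call interval. *Two weekly* can mean two calls a week apart (c = 7) or a call every two weeks (c = 14); the Summary's weeks 8 and 10 match the second.

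| s | i | Third session (day) | Last call, c = 7 | Last call, c = 14 |
|---|---|---|---|---|
| 0 | 7 | 14 | day 28 (4.0 wk) | day 42 (6.0 wk) |
| 0 | 10 | 20 | day 34 (4.9 wk) | day 48 (6.9 wk) |
| 7 | 7 | 21 | day 35 (5.0 wk) | day 49 (7.0 wk) |
| 7 | 10 | 27 | day 41 (5.9 wk) | day 55 (7.9 wk) |
| 14 | 7 | 28 | day 42 (6.0 wk) | day 56 (8.0 wk) |
| 14 | 10 | 34 | day 48 (6.9 wk) | day 62 (8.9 wk) |

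The last row overruns the stated 4 weeks of sessions (34 > 28 days). In the other five rows, calls one week apart end by day 42, so all five contacts can precede week 7. Calls two weeks apart end by day 42 only in the first row; elsewhere they overrun the stated 6 weeks, and in some rows they run past week 7.

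**4. Weight of the calls.** Section 6 gives 30–40 min per session (three: 90–120 min) and 10–20 min per call (two: 20–40 min). The calls' share of contact time is:

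- lowest: 20 / (20 + 120) = 14%
- midpoints: 30 / (30 + 105) = 22%
- highest: 40 / (40 + 90) = 31%

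The extremes pair short calls with long sessions and the reverse. Nurses may also adjust session length, so the range is indicative only.

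**5. T2.** Taking 3 months as 13 weeks (assumption):

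- end in week 6: 6 + 13 = week 19
- end in week 10: 10 + 13 = week 23
- stated in Randomization & blinding: week 12, which is 12 − 6 = 6 weeks after the first end date or 12 − 10 = 2 weeks after the second

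**The case against.** The strongest reply is that the out-of-line weeks stand in the Summary alone. The section that actually describes the intervention puts all contacts inside 6 weeks, and on that reading a week-7 T1 follows completion. A reader of the Summary might infer that T1 cannot measure the completed intervention. The documents do not support that as a general statement: it holds on the Summary's weeks and fails on Section 6 with weekly calls. A reader might also infer that every section labels week 7 as post-intervention. Only Sections 1, 5 and 7 do; Randomization & blinding gives the bare week.

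Two further inferences go too far. One is that the week-7 comparison is invalid. It remains a randomised comparison at a fixed time in both arms; what is in doubt is its label and meaning. The other is that T1 and T2 will be contrasted as initial effect and then maintenance. No such comparison is planned.

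It is also fair to say that patients in one arm receiving different schedules is a risk, not an established fact. There are three intervention nurses with training, a manual, a logbook of dates and weekly review by the principal investigator. These controls make drift between nurses less likely, but they do not say which schedule is to be followed.

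What stands is the contradiction itself, the ambiguous call spacing, and an end date on which both T1 and T2 depend.

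**Conclusion.** The concern holds as an internal inconsistency with consequences for how T1 and T2 are read. On the Summary's weeks, 3 of 5 contacts precede T1 and the last falls three weeks after it, so T1 would be a mid-intervention measure reported as post-intervention. On Section 6 with calls one week apart, all five contacts can precede T1; with calls two weeks apart, it depends on the start day and spacing. The documents do not settle which applies.

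T2 is the more consequential part, because the sample size is based on the 3-month comparison. Its possible dates are week 12 as stated, about week 19, or about week 23, the last two resting on 3 months being 13 weeks. This point does not alter the sample-size calculation.

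**What to change.** Reconcile Section 1, Section 6 (Intervention group) and Table 1 to one schedule of sessions and calls, and replace *two weekly* with an explicit interval. This review does not say which schedule is right.

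Then state T1 and T2 each as one fixed number of weeks from randomisation, identical in both arms, and carry those numbers through Section 1, Section 5, Section 6 (Randomization & blinding) and Section 7. Counting from randomisation matters because the control arm has no intervention contacts from which to count an end.

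Set the two times together. If the Summary's weeks were kept and T1 were moved to the week after the last call, T1 would be week 10 + 1 = 11, one week before the week-12 collection.

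If any scheduled call still falls after week 7 and T1 stays there, label T1 an interim assessment after the face-to-face sessions and do not report it as a post-intervention effect.

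The cost is a wording amendment and a possible shift of the assessment weeks. If T2 were placed three months after the end, follow-up would run 19 − 12 = 7 to 23 − 12 = 11 weeks beyond week 12. No patients, visits or staff are added and the sample size does not change. The change is best made before enrolment, because an assessment taken at the wrong time cannot be repeated.

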Three clinical nurse specialist as a part of research team from NCCCR will deliver the intervention. Nurses' inclusion criteria are (1) Senior clinical nurses with a Master degree or above, (2) having at least 3 years of working experience in HMC, (3) taking on chronic disease management in routine work, and (4) not planning to quit the job in the next 6 months and Nurses who are participating in other research studies on chronic disease management at the time of this study will be excluded. Nurses will recruit participants through approaching potentially eligible participants in NCCCR. Centre appointments by Clinical nurse specialists will be arranged for interested participants and the principal investigator/ co-investigator will determine the eligibility of participants, describe the study to them, obtain written consent forms, and collect baseline data. A one-week period will be allowed for participants to decide whether or not they wish to participate in the study. Participants' reasons for nonparticipation will be recorded.

Sample size; data collection methods

Sample size

Sample size calculation was performed using G*Power Version 3.1.9.7. Estimation is based upon the primary outcome, medication adherence, at 3 months of follow-up between the intervention and control group. Medication adherence is calculated as sum of the scores from each item using Morisky 8. Based on our recent systematic review and meta-analysis on medication adherence interventions among patients with multimorbidity Cohen's effect size (d) of 0.52 on medication adherence is estimated for a medication self-management intervention program. The required sample size will be 94 participants (47 in the intervention group and 47 in the control group) to attain an 80% power with a two-sided α of 0.05. Therefore, for a 5% attrition rate, the final sample size required is 100 participants.

For Arabic speaking patients, the questions will be translated to Arabic by the Arabic speaking research team member.

Randomization & blinding

Consenting participants will be randomized in outpatient clinic in NCCCR. Randomization will be block randomization, and generated by a computer program centrally (Nursing/ Midwifery Research department).

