Our primary analysis will be the ‘intention-- to-treat’ population, which will include all randomized patients analyzed according to their original treatment allocation, irrespective of their subsequent adherence or how they were actually treated. All data will be analyzed using STATA 17.0 software. Descriptive statistics will be used to describe and compare socio-demographic data on participants between the intervention and control group. Continuous variables that follow a normal distribution will be expressed as means and standard deviations, whereas categorical variables will be presented as frequency counts and percentages. Median values and interquartile ranges will be calculated for continuous data with a skewed distribution. Mann-Whitney U-test or t-test will be performed for continuous data to compare baseline characteristics between groups, and Chi-squared test or Fisher’s exact test will be used for categorical variables. The distributions of the outcome variables will be evaluated, and normalizing transformation will be applied as needed. Primary and secondary outcomes will be analyzed following the intention to treat principle at the individual participant level. Changes in repeated outcome measures across different time points between the intervention and control group will be analyzed using generalized estimating equation models with adjustment for potential confounders of the baseline variables. All statistical tests are two-sided, and $p < 0.05$ will be statistically significant.

9. Adverse Event Reporting

In this section, provide a definition of anticipated adverse events that are related to the research, including a description of how SAEs will be assessed, tracked and reported

There will not be any adverse events related to intervention because it is educational intervention. If some adverse event related to outcome reported during the study, we will notify to the IRB.

10. Ethical Consideration

A statement that the study will be conducted in full conformance with principles of the “Declaration of Helsinki”, Good Clinical Practice (GCP) and within the laws and regulations of MoPH in Qatar.

The study will be conducted in full conformance with principles of the “Declaration of Helsinki”, Good Clinical Practice (GCP) and within the laws and regulations of MoPH in Qatar.

11. Sponsor, Funding & Collaborator Information

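### The 94 evaluable patients match a one-sided test; at the stated two-sided α of 0.05 they give about 70% power for d = 0.52, not 80%

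*Combined protocol and SAP*

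**What the plan says.** The sample-size paragraph in section 6 of the combined protocol and SAP names G*Power 3.1.9.7 and gives a full set of inputs.

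- **Comparison:** "Estimation is based upon the primary outcome, medication adherence, at 3 months of follow-up between the intervention and control group".
- **Effect:** "Cohen's effect size (d) of 0.52 on medication adherence is estimated for a medication self-management intervention program", taken from a systematic review and meta-analysis by the trial team.
- **Result:** 94 evaluable patients, with 47 in the intervention arm and "47 in the control group) to attain an 80% power with a two-sided α of 0.05".
- **Attrition:** "for a 5% attrition rate, the final sample size required is 100 participants".

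Section 5 sets 1:1 allocation. Section 8 repeats the direction of testing for the analysis: "All statistical tests are two-sided", with significance at p < 0.05. The sample-size paragraph mentions no baseline correlation, no gain from covariates and no repeated-measures term.

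**The concern.** For a two-group comparison of means, a standardised effect, a power, an α and the number of sides fix the sample size. The five stated quantities (0.52, 80%, 0.05, two-sided, 47 per arm) do not fit together: 47 per arm is too small for the other four.

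The stated power is the justification for the size of the trial, on its primary outcome. Section 4 makes effectiveness on adherence the primary objective. If the true power is well below 80%, ethics reviewers and later readers are relying on a chance of detecting the planned effect that the design does not provide.

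**Working it through.** **Inputs.** d = 0.52, 80% power, α = 0.05 two-sided, 47 per arm and 5% attrition (section 6, sample size); 1:1 allocation (section 5); two-sided testing in the analysis (section 8). A standardised effect means SD = 1.

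**Step 1. Try to reproduce 47 per arm from the stated two-sided inputs.**

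Normal approximation: n per arm = 2(z₁₋α/₂ + z₁₋β)² / d²

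= 2(1.960 + 0.842)² / 0.52² = 2 × 7.849 / 0.2704 = 58.05, so 59 per arm (118).

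The exact calculation for an independent-samples t-test uses the noncentral t distribution with 2n − 2 degrees of freedom and noncentrality d√(n/2). It gives n = 59.03, so 60 per arm (120). At 59 per arm the power is 79.98%, just short; at 60 it is 80.6%. The stated 94 is not reproduced. The shortfall is 120 − 94 = 26 evaluable patients, too large to be rounding or a choice of approximation.

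**Step 2. Try a one-sided α of 0.05.**

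Normal approximation: 2(1.645 + 0.842)² / 0.2704 = 45.73, so 46 per arm.

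Noncentral t: n = 46.42, so 47 per arm, or 94 in total. This is the protocol's figure exactly. One-sided power is 79.7% at 46 per arm and 80.4% at 47.

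**Step 3. Two-sided power that the planned numbers give.**

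At 47 per arm the noncentrality is 0.52 × √(47/2) = 2.521, with 92 degrees of freedom and a two-sided critical value of 1.986.

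| Evaluable per arm | Two-sided power, noncentral t | Two-sided power, normal approximation |
|---|---|---|
| 47 | 70.3% | 71.3% |
| 50 (no attrition) | 73.1% | 73.9% |
| 60 | 80.6% | not computed |

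Type II error at 47 per arm is 100 − 70.3 = 29.7%, against 20% stated.

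**Step 4. Effect detectable with 80% two-sided power at 47 per arm.**

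Solving the noncentral t for d gives 0.584. Relative to plan: 0.584 / 0.52 = 1.12, about 12% larger.

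**Step 5. Attrition.**

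94 / 0.95 = 98.9, so 100 randomised is sound for 94 evaluable. For 120 evaluable, 120 / 0.95 = 126.3, so 127. With equal arms, 60 / 0.95 = 63.2, so 64 per arm (128).

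**Step 6. Other two-sided calculations that might have given 94.**

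- Mann-Whitney test: 62 to 69 per arm, using asymptotic relative efficiencies of 0.955 and 0.864. This needs more patients, not fewer.
- Baseline-adjusted comparison, with the effect scaled to d/√(1 − ρ²): power at 47 per arm is 72.1% for ρ = 0.2, 74.4% for ρ = 0.3, 79.8% for ρ = 0.45 and 82.1% for ρ = 0.5. These correlations are assumptions; the protocol gives none.
- Repeated-measures between-group test: close to 94 in total (96) only with an assumed correlation of 0.6 for two measures or 0.7 for three.

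None of these is described in the sample-size paragraph.

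**The case against.** The strongest reply is that 70.3% belongs to an unadjusted t-test at one time point, whereas section 8 plans a generalized estimating equation model on repeated measures, adjusted for baseline variables. That analysis could have more power. With covariates correlating at 0.45 with the outcome, power at 47 per arm would be 79.8%. Using two follow-ups could also approach 80%, if the effect were 0.52 at both.

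This limits what the 70% describes, but it does not rescue the 94. The sample-size paragraph claims no such gain. The gain would also be hard to obtain from baseline adherence: section 6 restricts entry to a Morisky score of zero (in the inclusion list) or below 2 (in the text above it), on the same 0 to 8 scale as the primary outcome. If everyone scores zero, baseline adherence has no variance and adjusting for it gains nothing; below 2, its range is very narrow. Other covariates would have to supply the correlation, and no evidence for that is offered.

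Two further points deserve weight. The one-tailed setting is an inference from an exact match, since the protocol names neither the test nor the tails option. That stands, but the error does not depend on the explanation. The title also calls this a feasibility trial, where formal power matters less. Yet the stated aim and primary objective are effectiveness, and the protocol makes a formal power claim, which should be right.

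**Conclusion.** The concern holds; the power statement is wrong as written. The stated inputs require 60 per arm, not 47. For the comparison the protocol describes, two-sided power is 70.3% with 94 evaluable and 73.1% if all 100 are analysed, about 10 and 7 percentage points below the stated 80%.

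This rests on a two-sample t-test with equal arms, no covariate adjustment and d = 0.52 taken as given. The normal approximation changes the figures by about one point. The type I error is not affected, because the analysis is two-sided as stated.

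**What to change.** Correct the sample-size paragraph in section 6 and keep the tests two-sided. The sponsor has two coherent options.

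1. **Keep 100 randomised and restate the power.** Suggested text: *With 94 evaluable participants (47 per arm), a two-sided test at α = 0.05 has about 70% power to detect a standardised difference of 0.52 and about 80% power to detect 0.58.* This costs one sentence and no extra patients; the stated power becomes less favourable. It is the minimum correction.
2. **Keep 80% power for d = 0.52 and enlarge the trial.** This needs 120 evaluable, and 127 randomised at 5% attrition (128 for equal arms). The cost is 27 or 28 more patients than the planned 100.

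If the sponsor prefers to rely on the adjusted model, the paragraph should state the assumed correlation and its source, and show the power across a range of values.
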